12.3.4.6. Potential Effect on Hepcidin and Iron Metabolism

The effect on Hepcidin and Iron Metabolism will be assessed using the mean change from baseline over time in Hepcidin and Iron parameters.

Hepcidin Levels

Hepcidin levels will be measured at screening, week 1 day 1, week 5, week 13, week 21, week 25, week 28, week 39 and week 52 (or EOT).

Absolute value and mean change from baseline in hepcidin at each time point will be summarized using descriptive statistics. The analysis windows are defined in [Appendix 19.3.1](#). The summary will include:

- Change from baseline in hepcidin
- Change from baseline in hepcidin stratified by TI vs. Non-TI (TI will be defined by week 28 as for the primary endpoint)
- Correlation between change from baseline in hepcidin and change from baseline in Hb. A scatter plot will be provided with CFB in Hepcidin on x-axis and CFB in Hb on y-axis. Different colors

will be used to indicate two treatment groups. A fitted linear regression line will be added to the scatter plot as well as the spearman correlation coefficient and p-value.

Treatment comparison will be based on a MMRM model with treatment group, visit, treatment*visit as fixed effect, baseline hepcidin value as covariate, controlling for stratification factors. The LSM and the corresponding 95% confidence intervals for the differences between roxadustat and the placebo group (roxadustat – placebo) will be presented along with the p-values for the treatment differences resulting from the model. Missing data will be handled by the MMRM model.

Week 28 and week 52 are the analysis endpoint for 28-week and 52-week analysis respectively; the p-values will be reported.

The analysis will be conducted for FAS population.

Iron Parameters

Iron biomarkers will be measured at screening, week 1 Day 1, week 3, week 5, week 9, week 13, week 17, week 21, week 25, week 28, week 39 and week 52 (or EOT).

Absolute value and mean change from baseline in iron parameters (Transferrin, TIBC, UIBC, TSAT and Ferritin, serum iron) at each time point will be summarized using descriptive statistics. The analysis windows are defined in [Appendix 19.3.1](#).

Treatment comparison will be based on a MMRM model with treatment, visit, treatment*visit, and stratification factors as fixed effects, the baseline value as covariate. The LSM and the corresponding 95% confidence intervals for the differences between roxadustat and the placebo group (roxadustat – placebo) will be presented along with the p-values for the treatment differences resulting from the model.

Week 28 and week 52 are the analysis endpoint for 28-week and 52-week analysis respectively; the p-values will be reported.

The analysis will be conducted for FAS population.

12.3.4.7. Effect on Cholesterol and Lipid Parameters

The effect on cholesterol and lipid parameters will be assessment by mean change from baseline over time in cholesterol and lipid parameters.

Absolute value and mean change from baseline in total cholesterol at each time point will be summarized using descriptive statistics. The definitions of analysis widows are defined in [Appendix 19.3.1](#).

The total cholesterol will be analyzed similarly using the MMRM method. The LSM and the corresponding 95% confidence intervals for the differences between roxadustat and the placebo group (roxadustat – placebo) will be presented along with the p-values for the treatment differences resulting from the model.

Other Serum Lipid Panel (non-fasting) parameters includes LDL, HDL, LDL/HDL ratio and triglycerides (TG), summary of mean change from baseline over time will use the same method as that for total cholesterol.

Week 28 and week 52 are the analysis endpoint for 28-week and 52-week analysis respectively; the p-values for other visits are for reference only.

For the analysis of triglycerides data, due to the nature of the skewness for the triglycerides data, the stratified non-parametric ANCOVA as that described in [Section 12.3.3.3](#) with baseline value as the covariate will be used for the analyses.

12.4. Examination of Subgroups

Subgroup analyses (based on the FAS) will be performed based on the following criteria using the same approach as for the primary efficacy endpoint:

- by gender: male, female
- by age: < 65, >= 65 years
- by race: white, non-white
- by baseline endogenous EPO level: ≤ 200 mIU/mL, > 200 and ≤ 400 mIU/mL (defined as an exploratory endpoint in [Section 12.3.4.5](#))
- by IPSS-R risk category: low risk / very low risk, intermediate risk
- by RBC transfusion burden: 1 pRBC/8-weeks over 16 consecutive weeks, 2- 4 pRBC/8-weeks
- by baseline iron repletion status ([TSAT < 20% or ferritin < 100 ng/mL] vs. others),
- by baseline CRP group (CRP \leq ULN vs. CRP > ULN)
- by Prior ESA use: (ESA Naïve vs. ESA Experienced)
- by region (Section 12.5)

Subgroup analysis will also be performed based on anticoagulant use at baseline if applicable. For the mentioned subgroup analyses, un-stratified tests/models can be used to evaluate the treatment differences if the sample size within a level of a subgroup does not allow for a comparison. If the subgroup variable is the same as the stratified variable, the corresponding stratified variable will be dropped from analysis. If the strata contain few or no patients, the stratification variable will not be included in the analysis.

Patients with missing baseline values used to define the subgroups will be considered in a subgroup category missing, otherwise data will be excluded from the respective subgroup analyses.

12.5. Subgroup Analyses by Region

As it is expected to have approximately 100 global sites in this study, sensitivity analyses for the primary and secondary endpoints will be performed adding region and region by treatment interaction term in the model in order to examine whether the treatment effect varies by region and if results adjusted by region are consistent with those from the corresponding primary analysis and secondary analyses. Sites will be pooled by country into geographic region (defined as North America, Europe and Asia-pacific) to enable these analyses.

In addition, the consistency of the treatment effect across region will also be assessed by performing a subgroup-type analysis with respect to the primary and secondary endpoint, with region treated as subgroups. A listing of TI response rates will be provided by individual study site.

For NDA filing in China, the above analyses by additional region subgroup (defined as East Asia, non-East Asia) will also be provided.

13. PHARMACOKINETICS / PHARMACODYNAMICS ANALYSES

The methods described in [Appendix 19.2](#) will be used.

14. SAFETY ANALYSES

All safety analyses will be conducted using the safety population. Percentages will be calculated based on the number of patients in the safety population.

For open-label component, the summaries will be presented by dose level cohort. For OL high-erythropoietin component, the summaries will be presented along with the cohorts from open-label component. For double-blind component, the summaries will be presented by treatment group.

14.1. Adverse Events

A treatment-emergent AE (TEAE) is defined as an AE that begins on or after the first dose of study treatment and within 28 days of the end date of the last dose of study treatment. An adverse event with unknown onset date will be counted as TEAE unless the event is resolved prior to the first dose of study medication.

Adverse events will be coded using the Medical Dictionary for Regulatory Activities (MedDRA, version 19.1). CTCAE Version 4.03 will serve as guidance for specific severity assessment criteria for AEs. Any adverse event recorded prior to the start of study treatment will be listed together with all other adverse events. Only treatment-emergent adverse events will be summarized.

If a patient has more than one TEAE coded to the same preferred term, the patient will be counted only once for that preferred term. Similarly, if a patient has more than one TEAE within a system organ category, the patient will be counted only once in that system organ category.

In this analysis, if a patient reports multiple occurrences of TEAEs within one system organ class or preferred term, the most closely related occurrence will be presented. TEAEs with unknown relationship to study treatment will be counted as “possibly related” in the summary table but will be listed with a missing relationship in data listing.

In this analysis, if a patient reports multiple occurrences of TEAEs within one system organ class or preferred term, the most severe occurrence will be presented in the table summarized by maximum severity. TEAEs with unknown severity will be counted as “Severe” in the summary table but will be listed with a missing severity in data listing.

The overview table by treatment and overall will be summarized showing the number and percentage of patients with at least one AE in any of the following categories:

- TEAEs
- drug related (Possibly Related and Related) TEAEs
- all grade 3 or greater TEAEs
- Serious TEAEs
- TEAEs leading to discontinuation of study treatment
- TEAEs leading to death
- TEAE of special interest

In summary, the following sets of adverse events will be summarized separately in separate tables by SOC (sorted alphabetically) and PT (sorted by descending) that present the number and percentage of patients with:

- any TEAE (number of patients who have at least one adverse event)

- TEAE by maximum severity
- TEAE with relationship to study medication suspected to be related to study drug
- all grade 3 or greater TEAE
- treatment-emergent serious AEs (TESAE)
- TEAEs leading to discontinuation of study treatment,
- TEAEs leading to death
- TEAE of special interest
- TESAE leading to discontinuation of study treatment

AE of special interest consists of the following categories: Secondary hypothyroidism, Thyroid disorders (Hypothyroidism and Hyperthyroidism), Dermatitis Exfoliative Generalised, Deep vein thrombosis, Pulmonary embolism, Cardiovascular events (cardiac failure, arrhythmia, myocardial infarction), Seizures, Serious infections. Number and percentage of patients with any TEAE of special interest will be summarized up to 28 weeks, 52 weeks and 52 weeks and beyond. Exposure adjusted incidence rate (EAIR) of TEAE of special interest per 100 patient exposure years will also be presented. See [Section 14.1.2](#) for EAIR calculation.

In addition, most frequently occurring adverse events ($PT \geq 5\%$ of patients in any dose cohort/treatment group) and most frequently occurring non-serious adverse events ($PT \geq 5\%$ of patients in any dose cohort/treatment group) for each PT will be summarized in descending frequency according to its incidence in either dose cohort/treatment group.

In addition, the incidence rate $\times 100 / PEY$ will be presented along with the number and percentage of patients in double-blind tables, where Patient-Exposure-Year (PEY) = (Last Dose Date - First Dose Date + 1)/365.25.

All AEs will be presented in a listing, including patient identifier, treatment group, system organ class, preferred term, start and stop dates, seriousness, severity, relationship to study treatment, Action taken with regard to study drug and outcome. Additionally, listings of SAEs, Death and AEs leading to permanent discontinuation of study drug and AEs of special interest will be presented. The listing of AEs prior to start of treatment will be provided for all patients enrolled.

Listings of death report will be provided in the SAF with death date, primary cause of death and verbatim, system organ class and preferred term of AE leading to death.

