### 7.2 Definitions

#### 7.2.1 Definition of an Adverse Event

An AE is any untoward medical occurrence associated with the use of a drug in humans, whether or not considered drug-related.

An AE can be any unfavorable and unintended sign, symptom, or disease temporally associated with the use of a drug, without any judgment about causality. This includes any occurrence that is new in onset or aggravated in severity or frequency from the baseline condition. An AE can arise from any use of the drug (e.g., off-label use, use in combination with another drug) and from any route of administration, formulation, or dose, including an overdose.

An AE includes medical conditions, signs, and symptoms not previously observed in the patient that emerge during the protocol-specified AE reporting period, including signs or symptoms associated with an underlying condition that were not present prior to the AE reporting period ([Section 7.3.1](#)).

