### **7.3 Procedures for Eliciting, Recording, and Reporting Adverse Events**

#### **7.3.1 Adverse Event Reporting Period**

The study period during which all AEs and SAEs must be reported begins after informed consent is obtained and ends 28 days after the last study visit, except for pregnancy reporting (Section 7.3.6).

Adverse events will be followed until resolved, stable, or until the patient’s last study visit or lost to follow-up. If an AE is not resolved or stabilized at the patient’s last visit, it is up to the discretion of the investigator and study Medical Monitor to determine if further monitoring of the event is warranted.

Adverse events collected prior to dosing of study drug will be considered “nontreatment emergent” while those reported after the first dose of study drug and up to 28 days after the last dose of study drug will be considered “treatment emergent” and be assessed for relationship to study drug. If an AE starts on Day 1, the investigator must assess as to whether the AE started prior to or after the administration of study medication and record accordingly.

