### **8.3.6 Summary of Safety Data**

Summary of safety data will be based on the Safety Population. Safety parameters include adverse events, N (%) patients progressing to AML, laboratory parameters, vital signs, ECG parameters, prior and concomitant medication use. For each safety parameter, the last assessment made prior to the first dose of study treatment will be used as the baseline, unless otherwise specified. In general, safety data will be summarized descriptively; no inferential statistical procedures will be applied.

Adverse events will be coded using Medical Dictionary for Regulatory Activities (MedDRA). A treatment emergent adverse event (TEAE) is defined as any new or worsening of an existing condition occurred after the first dose of the study medication and within 28 days after the last dose of study medication. TEAEs will be tabulated to examine their frequency, severity, organ systems affected and relationship to study treatment. Deaths, SAEs, AEs leading to study or treatment discontinuation, and AEs of special interest will be listed or tabulated separately.

Laboratory tests, vital sign measurements, ECG parameters, as well as the changes from baseline will be summarized descriptively by assessment time point. Clinically significant changes from baseline in these safety parameters will be identified. Shift tables will summarize changes for selected laboratory measures.

Medications used prior to and during the study will be coded using The World Health Organization Drug Dictionary (WHODrug). Prior and concomitant medications will be tabulated by therapeutic class and generic name.

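### SAP 14.1 defines a TEAE by start date alone, so a pre-dose AE that worsens on treatment is missed in the AE tables if it keeps its original start date

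*SAP*

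**What the plan says.** The definitions do not agree.

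- **SAP 14.1:** "A treatment-emergent AE (TEAE) is defined as an AE that begins on or after the first dose of study treatment", up to 28 days after the last dose. Worsening is not mentioned.
- **Protocol 8.3.6:** a TEAE is "any new or worsening of an existing condition occurred after the first dose of the study medication", with the same 28-day limit.
- **Protocol 7.3.1:** "Adverse events collected prior to dosing of study drug will be considered" non-treatment-emergent; those reported from first dose to 28 days after the last dose are treatment-emergent. There is no exception for an early event that later worsens.

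The SAP definition decides what is tabulated: "Only treatment-emergent adverse events will be summarized". Events from before treatment go to listings: "Any adverse event recorded prior to the start of study treatment will be listed together with all other adverse events".

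Collection starts before dosing. Under Protocol 7.3.1 the reporting period "begins after informed consent is obtained and ends 28 days after the last study visit".

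**The concern.** In a placebo-controlled safety comparison, an existing complaint that becomes severe or serious on study drug belongs in the tables beside new events. Protocol 8.3.6 provides for that; the SAP wording does not. Since tabulation is restricted to TEAEs, the definition controls the overview, maximum severity, grade 3 or higher, serious, related, discontinuation, death, special-interest and subgroup tables, and the EAIR.

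Pre-dose AE records are to be expected. AEs are collected from consent, and SAP 3.1 allows baseline assessments up to 42 days before the first dose. The SAP plans a listing of AEs from before treatment, and SAP 19.3.3 has a rule for missing severity in AEs that started before the first dose.

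The gap also sits oddly with the SAP's other conventions, which lean towards inclusion. An AE with unknown onset counts as a TEAE unless it resolved before the first dose; unknown severity counts as severe; unknown relationship counts as possibly related. An event known to have worsened on drug has no comparable protection.

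**Working it through.** The plan states no figure to reproduce. The check is to follow one event through the written rules: an AE that starts after consent and before the first dose, and worsens or becomes serious after it.

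**Path A: one record, original start date kept.**
1. The start date precedes the first dose, so the SAP 14.1 definition is not met.
2. Only TEAEs are tabulated, so the event enters no TEAE-based table, whatever its later grade or seriousness.
3. It still appears in the AE listing with dates, severity and seriousness and, where it qualifies, in the SAE, death or discontinuation listings.

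**Path B: the worsening entered as a new AE with its own onset date.**
1. The new start date is on or after the first dose, so the definition is met (given the 28-day limit).
2. The event is tabulated.

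**Which path do the documents prescribe?**
- Protocol 7.2.1 makes an aggravation an AE in its own right: "This includes any occurrence that is new in onset or aggravated in severity or frequency from the baseline condition". This supports B.
- Protocol 7.3.2 has baseline conditions reported as AEs once they worsen significantly. This supports B.
- Protocol 3.5 treats significant pre-dose findings as baseline medical history, and Protocol 6.1.1 and 6.1.2 send screening AEs there where applicable. A history item that worsens would then be a new AE. This supports B, but the transfer is conditional.
- Protocol 7.3.1 labels AEs collected before dosing non-treatment-emergent with no worsening exception. This is compatible with A.
- Neither document says whether an AE already on record is updated, or closed and re-entered, when it worsens.

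The outcome for such a record therefore depends on data-entry practice.

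**Consequence for EAIR.** SAP 14.1.2 sets time at risk for a patient with an event at (first event date − first dose date + 1)/365.25. For a start date *d* days before the first dose this is (1 − *d*)/365.25: zero at *d* = 1 and negative for larger *d*. For a worsening *w* days after the first dose it is (*w* + 1)/365.25, which is positive. Adding worsening to the definition without a new date would break the rate.

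**Scale per patient (illustration only).** SAP 17 gives 140 double-blind patients. Assume an exact 3:2 split, all treated: 84 roxadustat and 56 placebo.
- One omitted patient moves an incidence by 1/84 = 1.2 percentage points on roxadustat, or 1/56 = 1.8 on placebo.
- The most-frequent-AE tables use a 5% threshold in any group. Within an arm that needs 5/84 = 6.0% (4/84 = 4.8% falls short) or 3/56 = 5.4% (2/56 = 3.6% falls short). One omission could drop a preferred term from the table if the other arm is also below 5%.

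How many such events to expect is not stated and cannot be derived.

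**The case against.** The strongest reply is that the gap rarely bites. The protocol's recording rules mostly favour entering a worsening as a new AE, which the SAP counts. The protocol is not uniform either: 7.3.1 is close to the SAP wording, so this is not simply a SAP departing from its protocol. The listings keep the event visible, and AML progression, laboratory and liver abnormalities, excessive hematopoiesis, vital signs, ECG and ECOG are summarised without reference to TEAE status. Finally, the AE attributes in Protocol 7.3.2 include onset and resolution dates but no date of worsening, so a SAP sentence alone could not supply one.

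Most of this stands. It makes the omission conditional and shows that the repair needs a recording rule as well as a definition. It does not remove the difference between SAP 14.1 and Protocol 8.3.6, nor the absence of any instruction for a pre-dose AE record that worsens.

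A reader might infer three stronger things that the documents do not support:

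- **That every such AE is left out of every summary.** This follows only on Path A, which no section prescribes.
- **That the SAP changed the definition without declaring it.** SAP 1 says the plan follows Amendment 03 of 30 January 2020; the protocol available is Amendment 02. The SAP 17 text available starts at item 3. Non-declaration cannot be shown.
- **That the difference between arms is understated.** That would require worsening to be more frequent on roxadustat. Nothing in the documents speaks to this.

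**Conclusion.** The point holds in conditional form. SAP 14.1 is narrower than Protocol 8.3.6 (Amendment 02) because it lacks the worsening limb, and the protocol is itself inconsistent because 7.3.1 lacks it too. Since only TEAEs are tabulated, a pre-dose AE that worsens or becomes serious on treatment is omitted from the TEAE-based tables and EAIR if kept under its original start date. It is counted if entered as a new AE, and listed in both cases.

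The number of patients affected, and the size and direction of any effect on the comparison between arms, are undetermined. The only scale available is 1.2 or 1.8 percentage points per omitted patient, on the assumed 84:56 split. The conclusion assumes that Amendment 03 did not alter Protocol 8.3.6 or supply a recording rule, which cannot be checked. The correction is worth making because inclusion in the safety tables should not depend on how a site enters a worsening.

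**What to change.** 1. **SAP 14.1:** define a TEAE as an AE that begins, or worsens in severity or becomes serious, on or after the first dose and within 28 days of the last dose.
2. **Recording convention (SAP and eCRF completion guidelines):** a post-dose worsening of a pre-dose AE is entered as a new AE dated at the worsening, and that date is used as the event date for EAIR in SAP 14.1.2.
3. **Protocol 7.3.1:** align with 8.3.6, so that an AE collected before dosing is non-treatment-emergent unless it worsens after the first dose.
4. Check the wording against Amendment 03, and list the definition in SAP 17 if it differs from that version.

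The cost is one SAP sentence, the recording convention and a flag in the AE dataset. Records already held as a single entry would need a site query for the date of worsening, because that date is not among the listed AE attributes. AE percentages may rise slightly in both arms.

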### **3.5 Safety Monitoring Plan**

Safety will be assessed throughout the study. A complete baseline profile of each patient will be established through demographics, medical history, clinical laboratory values, vital signs, physical examination (PE), and electrocardiogram (ECG). During the course of the study, vital signs and laboratory tests will be performed at regular intervals as described in schedule of assessments ([Appendix A](#) and [Appendix B](#)).

Blood pressure (BP) and heart rate (HR) should be assessed according to the guidelines described in [Appendix N](#).

A physical exam (PE) will be conducted during Screening, Day 1, Week 28, EOT and at the 4 Week post-EOT visit.

Any significant findings prior to administration of study drug will be considered as baseline conditions and will be captured as baseline medical history. Any clinically significant (CS) changes from baseline will be monitored throughout the study and appropriate interventions will be taken accordingly. Clinical laboratory tests may be assessed at additional times on unscheduled visits for safety reasons. Liver function abnormalities will be monitored according to drug-induced liver injury (DILI) guidance ([Appendix H](#)).

All adverse events (AEs), serious AEs (SAEs), and ongoing concomitant medication usage will be monitored and recorded throughout the study. SAE reports will be evaluated individually to assess the impact of the event, if any, on the overall safety of the product and on the study itself. Cumulative AEs will be monitored throughout the study. SAEs and AEs will be followed until resolved, deemed stable, or until the patient's 4-week post EOT visit. See [Section 7](#) for details on AE and SAE reporting.

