### 4.3 Treatment Discontinuation

Patients who discontinue study medication early (for any reason) will remain in the study through the 52 week study period. Patients will have a 4 week follow-up visit after stopping study medication and then be followed up at a reduced visit schedule of every 8 weeks until the end of the study.

Patients will be discontinued from treatment for the following reasons (below and [Appendix H](#) and [Appendix O](#)):

- a. Disease progression: Diagnosis of AML during the study
- b. Liver Function: Discontinuation of treatment will occur if:
  - ALT or AST  $>8 \times$  ULN
  - ALT or AST  $>5 \times$  ULN for more than 2 weeks
  - ALT or AST  $>3 \times$  ULN and TBL  $>2 \times$  ULN or international normalized ration (INR)  $>1.5$  (If INR testing is applicable/evaluated)
  - ALT or AST  $>3 \times$  ULN with the appearance of fatigue, nausea, vomiting, right upper quadrant pain or tenderness, fever, rash and/or eosinophilia ( $>5\%$ )

A patient who decides to discontinue treatment with study medication will always be asked about the reason(s) for discontinuation and the presence of AEs (if any). These data will be ascertained and documented by the investigator and recorded in the electronic case report forms (eCRF) as appropriate. The patient should return all study medications.

Reasons for permanent discontinuation of treatment with study medication:

- Patient's decision (subject no longer wants to continue study medication (i.e., withdrawal of consent)
- Investigator's decision that it is in the best interest of the patient to be withdrawn from the study
- AEs (including SAEs)
- Significant noncompliance with study procedures, as determined by Investigator or Sponsor
- Lack of efficacy
- Treatment with ESAs
- Patient is lost to follow-up
- Site terminated by the Sponsor
- Pregnancy
- Death

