Week 28 visit: Week 28 visit should be conducted at the end of 28 weeks of treatment (2 weeks after Week 27 Visit). Primary analysis of efficacy will be conducted when all the randomized (DB) patients complete 28 weeks of treatment or are discontinued from study medication before this time. **End-of-Treatment (EOT/ET) Visit:** Patients who complete 52-week treatment period or discontinue study medication early (Early Termination before week 52) will have an EOT/ET visit.

Post-Treatment Follow-Up Period: Week 56 (Post-EOT Week 4)

Post-Treatment Follow-Up Period for ET Patients: Patients who discontinue early will have visits every 8 weeks until Week 52.

End of Study (EOS) Visit: All patients who complete 52 weeks (of treatment with study medication) will undergo a 4 week follow-up period after the last dose of study medication and will return for the End of Study (EOS) visit. Patients who discontinue study medication early (for any reason) will remain in the study through the entire 52 week study period. Patients will have a 4 week follow-up visit after stopping study medication/ET visit and then be followed up at a reduced visit schedule of every 8 weeks until the end of the study.

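### SAP Section 14 specifies no by-arm table of all deaths, or of SAEs starting more than 28 days after last dose, through Week 52

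*SAP*

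**What the plan says.** **Follow-up and collection**
- Protocol 4.3: "Patients who discontinue study medication early (for any reason) will remain in the study through the 52 week study period". SAP 3.1 adds the schedule: "Patients who discontinue early will have visits every 8 weeks until Week 52".
- Protocol 7.3.1: reporting of AEs and SAEs starts after consent and "ends 28 days after the last study visit". Protocol 7.3.5.2 requires every death during participation to be reported as an SAE. Appendix B shows AE recording continuing after end of treatment.
- Protocol 2.9 and SAP 4.3 both set 52 weeks as the period over which safety is assessed.

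**Tabulation**
- SAP 14.1 defines a treatment-emergent AE (TEAE) by its start date: from first dose to 28 days after last dose. It then says: "Only treatment-emergent adverse events will be summarized".
- The death rows by arm in SAP 14.1 are TEAEs that led to death. For deaths as such: "Listings of death report will be provided in the SAF with death date", together with cause.
- SAP 14.1.2 censors time at risk for exposure-adjusted rates no later than 28 days after last dose.
- SAP 6.2 tabulates study exits by arm and by the reason on the CRF. SAP 14.2 tabulates progression to AML by arm. Neither states a 28-day limit.
- Protocol 8.3.6 allows deaths and SAEs to be either listed or tabulated.

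**Following AEs to resolution**
- Protocol 3.5: "SAEs and AEs will be followed until resolved, deemed stable, or until" the visit 4 weeks after end of treatment. Protocol 7.3.1 takes the patient's last study visit as the end.

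**The concern.** The trial plans a year of safety follow-up for each patient and then sets its by-arm AE tables to time on drug plus 28 days. For a patient who stops early, most of the later follow-up feeds only listings. The SAP does use off-drug data for efficacy: SAP 12.3.3.1 counts transfusions after end of treatment in the analysis of transfusion independence at any time in the study. No matching by-arm safety summary exists for late SAEs or for all-cause death.

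At stake is a basic statement in the study report: how many patients died in each arm by Week 52, from what cause, and over how much follow-up. As specified, a reader would have to assemble it from a listing. Exposure-adjusted rates do not fill the gap. They allow for unequal time inside the window but cannot bring back events after it.

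A second, smaller matter is that two protocol sections give different ends for following AEs to resolution. For an early discontinuer these can be months apart.

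**Working it through.** The plan states no figure on this point, so there is none to reproduce. The check has three parts.

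**1. Which deaths reach a by-arm table**

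| Case | Where it appears by arm |
|---|---|
| AE starts on drug or within 28 days of last dose; patient dies of it at any later time | TEAEs leading to death (SAP 14.1) |
| Progression to AML | AML table (SAP 14.2), no 28-day limit stated |
| New AE starts more than 28 days after last dose and is fatal | No safety table. Listing only, plus disposition (SAP 6.2) if the CRF records death as the reason for leaving the study |

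The table list for the Week 28 analysis in SAP 19.9 follows the same pattern: a table of fatal TEAEs and none of all deaths.

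**2. How much planned time lies outside the window**

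Inputs: planned follow-up 52 weeks (Protocol 4.3, SAP 3.1); window 28 days = 4 weeks after last dose (SAP 14.1). For a last dose at week *t*:
- off-drug follow-up = 52 − t
- part covered by the TEAE tables = min(4, 52 − t)
- part outside = max(48 − t, 0)

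| Stop (week) | Off-drug weeks | Covered | Outside | Share of 52 weeks | Share of off-drug time |
|---|---|---|---|---|---|
| 8 | 44 | 4 | 40 | 77% | 91% |
| 28 | 24 | 4 | 20 | 38% | 83% |
| 40 | 12 | 4 | 8 | 15% | 67% |
| 44 | 8 | 4 | 4 | 8% | 50% |
| 48 | 4 | 4 | 0 | 0% | 0% |

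More than half of the off-drug time is outside for any stop before Week 44.

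The share for the whole trial needs a stopping rate and stopping times, which the documents do not give. Assume stops spread uniformly over 52 weeks. The mean time outside per early discontinuer is (48² / 2) / 52 = 22.15 weeks, and 22.15 / 52 = 0.426 of planned follow-up. With a proportion *d* stopping early, and 140 patients (SAP 17):

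| d | Share of all planned follow-up = 0.426 × d | Patient-years = 140 × d × 22.15 / 52.18 |
|---|---|---|
| 10% | 4% | 5.9 |
| 30% | 13% | 17.8 |
| 50% | 21% | 29.7 |

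Timing matters too. If stops averaged Week 20, all before Week 48, the factor is (48 − 20) / 52 = 0.538, giving 16% at d = 30% and 27% at d = 50%.

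These are shares of time, not of deaths. The documents give no off-drug death rate, so the number of deaths affected cannot be calculated.

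**3. The two ends of AE follow-up**

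For a stop at Week 8, Protocol 3.5 ends at Week 8 + 4 = Week 12 and Protocol 7.3.1 at Week 52, a gap of 40 weeks. For a patient who completes 52 weeks of treatment, the 4-week visit is the last study visit and the two coincide.

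**The case against.** The case for leaving the plan alone is substantial:
- **The SAP follows the protocol.** Protocol 8.3.6 uses the same 28-day window, allows deaths to be listed or tabulated, and keeps safety descriptive. Mortality is not among the safety assessments in Protocol 2.9 or SAP 4.3. All deaths will be listed with date and cause. This stands: the tables are an improvement, not the repair of an error.
- **The AE follow-up discrepancy is minor.** Protocol 3.5 points to Section 7 for details of AE and SAE reporting, and Section 7.3.1 leaves unresolved events at the last visit to the investigator and Medical Monitor. The supplied protocol is Amendment 02, while the SAP cites Amendment 03, so current wording cannot be checked. The discrepancy in the supplied text remains, but nothing shows that sites would act differently.

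Several stronger readings are tempting, and the documents do not support them:
- *A reader might infer that every death more than 28 days after last dose goes uncounted.* The cut-off is on AE onset, not on the date of death.
- *A reader might infer that patients who stop for toxicity and later die of it drop out of the count.* An event that began on drug is a TEAE and is counted if fatal.
- *A reader might infer that late deaths appear in no by-arm output at all.* The disposition table may show them. The CRF is not supplied, so this cannot be settled. As described, that table gives neither cause nor person-time, and a death after some other recorded exit would not appear as a death.
- *A reader might infer a bias in a known direction because placebo patients stop sooner.* The documents give no stopping rate by arm and plan no inferential comparison of mortality.
- *A reader might infer that follow-up to Week 52 is certain for all.* It is the plan. Unplanned unblinding ends participation (Protocol 4.6.2), and Protocol 4.3 foresees withdrawal of consent and loss to follow-up.

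**Conclusion.** The point holds as a gap in presentation. SAP Section 14 specifies no by-arm table of all deaths, or of SAEs starting more than 28 days after last dose, through Week 52, although those data are to be collected and safety is to be assessed over that period. The gap is confined to events that begin after the window.

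Its size for one patient is fixed by arithmetic: 40 of 52 planned weeks for a stop at Week 8, 20 of 52 for a stop at Week 28. For the trial it is about 4% to 21% of planned follow-up under assumed stopping rates of 10% to 50%, uniform over 52 weeks, and would be larger with earlier stops. No direction of bias can be claimed.

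The difference between Protocol 3.5 and 7.3.1 is real in the supplied text for early discontinuers and is a separate matter of wording.

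**What to change.** Add two descriptive tables to SAP 14.1, on the safety analysis set by treatment received, as SAP 5.3.2 requires for safety:
1. All deaths from first dose to end of study, split into within 28 days of last dose and later, with primary cause and person-time to Week 52.
2. All SAEs over the same period, with the same split applied to onset.

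Keep the TEAE tables unchanged. A footnote should say that the death table splits on date of death while the fatal-TEAE table selects on AE onset, so the two counts need not agree.

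Reconcile Protocol 3.5 and 7.3.1 on when AE follow-up ends for early discontinuers, after checking both against Amendment 03.

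The cost is two tables from data already collected and one aligned sentence. No alpha, visits or new data are needed. The small downside is that off-drug events are diluted by later therapies, which is why the split is shown.
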